5.5.2 Handling of Subject Withdrawals or Subject Discontinuation of Study Intervention

Participants withdrawn after randomization will not be replaced. Participants who are withdrawn voluntarily or by the investigator will be discontinued from the study.

Study staff will complete a study disposition form in the eCRF, indicating the reason for discontinuation.

If the patient is a patient from the school and/or is interested in following orofacial pain care at the Brotman Facial Pain clinic, will be referred to the faculty practice clinic front desk for information and to schedule an appointment if wants to.

Unblinding, if required, will be carried out according to the procedures described in Section 5.4.2. A participant who has an AE at the time of discontinuation will be followed until the event returns to baseline, resolves, or is stabilized. If the AE does not meet one of these outcomes within 30 days after discontinuation or the end of the study, the participant will be referred to an appropriate provider for continued medical care (See section 9.2).

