12.2 Sample Size Considerations

The sample size was calculated based on the primary objective to compare the percentage of participants who had at least 30% reduction in pain from baseline to end of the treatment between experimental groups. Gomez-Arguelles et al. reported a reduction in pain frequency in days from 12.26(SD, 3.86) at baseline to 5.16(SD, 2.16) after 12 weeks anticonvulsants therapy for a group of trigeminal neuropathic pain patients [47] The changes was estimated as a very large effect size Cohen's d=2.1. The effect size in the animal studies has also been shown to be extremely large, approximately of 7 SD [48]. We assume the proposed trial will have a large effect size with Cohen's d=.8 or OR=4.2. Based on this assumption and two-sided type I error of α =.05, a sample of n=36 will provide sufficient power (Power >80%) to detect a large effect size between two groups [49]. This effect size could be interpreted as that about 58% of the participants in intervention group will reach at least 30% reduction in pain scores at the end of treatment

while 25% occur in the placebo group. Considering a 15% overall dropout rate, we will recruit N=40 participants (20 in each experimental group).

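### At the plan's own 15% dropout, recruiting 40 leaves 34 completers rather than the 36 the calculation calls for (section 12.2; minor)

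*Combined protocol and SAP*

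**What the plan says.** Section 12.2 builds the sample size in three steps.

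- Target: testing at the two-sided 5% level, the section claims that "a sample of n=36 will provide sufficient power (Power >80%) to detect a large effect size between two groups". The effect is described as "We assume the proposed trial will have a large effect size with Cohen's d=.8 or OR=4.2", and translated into responder rates: "about 58% of the participants in intervention group will reach at least 30% reduction in pain scores at the end of treatment", against an assumed 25% on placebo.
- Allowance for loss and recruited number: "Considering a 15% overall dropout rate, we will recruit N=40 participants (20 in each experimental group").
- Section 5.5.2 adds that "Participants withdrawn after randomization will not be replaced".

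Sections 5 and 5.4.1 repeat 40 participants, 20 per arm, at 1:1. No section gives a dropout rate of 10% or another derivation of 40.

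**The concern.** The target, the dropout rate and the recruited number are linked by one multiplication, and the three stated values do not satisfy it. A trial that recruits as planned and loses exactly the share it expects to lose ends below the number on which section 12.2 rests its power. Because withdrawals are not replaced, the gap cannot be made up during the trial. This is the sample-size statement for the primary objective, and any reader can check it, so it should be right.

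**Working it through.** **Inputs.** Target n = 36 in total, dropout d = 0.15, N = 40 (20 per arm), two-sided alpha 0.05, responder rates 0.58 and 0.25, Cohen's d = 0.8: all from section 12.2. The 36 is read as a total because 40 is stated as 20 per arm.

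**1. Can N = 40 be reproduced?**

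- Correct inflation, n/(1 − d): 36/0.85 = 42.35, so 43, or 44 (22 per arm) at 1:1.
- The common but invalid shortcut, n(1 + d): 36 × 1.15 = 41.4, so 42.
- Neither gives 40. Exact matches are 36/0.90 = 40 (36 needed, 10% dropout) and 34/0.85 = 40 (34 needed, 15% dropout).

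**2. Forward check.** 40 × 0.85 = 34, or 20 × 0.85 = 17 per arm. The largest dropout that still leaves 36 is 1 − 36/40 = 10%.

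**3. Cost of 34 instead of 36, responder rates.** Normal approximation with pooled variance under the null: power = Φ[(p1 − p2 − 1.96·SE0)/SE1], where SE0 = √(2·p̄(1 − p̄)/n), SE1 = √([p1(1 − p1) + p2(1 − p2)]/n), p̄ = 0.415 and n is per arm.

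- n = 18: SE0 = 0.1642, SE1 = 0.1548; (0.33 − 1.96 × 0.1642)/0.1548 = 0.052; power 52.1%.
- n = 17: SE0 = 0.1690, SE1 = 0.1592; (0.33 − 1.96 × 0.1690)/0.1592 = −0.008; power 49.7%.
- Difference: 2.4 points.

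**4. The same cost for d = 0.8.** Two-sample t-test, noncentrality 0.8·√(n/2).

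- n = 18: noncentrality 2.400, 34 df; power 64.5%.
- n = 17: noncentrality 2.332, 32 df; power 61.9%.
- Difference: 2.6 points.

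**5. Does 36 carry the stated power?** Steps 3 and 4 already show that it does not: 52.1% or 64.5%, against a claim above 80%. Reaching 80% two-sided takes 34 per arm (68 in total) for the responder rates, or 26 per arm (52) by t-test for d = 0.8. Enrolling 44 and analysing all of them (22 per arm) gives about 61% for the responder rates.

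**The case against.** **Dropouts are not lost to the analysis.** Section 12.3 plans an intent-to-treat analysis by a generalized linear mixed model over baseline and Visits 2 to 4, with maximum likelihood under missing at random. Someone who leaves after Visit 2 or 3 still contributes. This stands in part. A reader might infer that only 34 people would be evaluable; the documents do not support that word, because no completers-only analysis is planned. The accurate term is participants completing Visit 4. The objection does not rescue N = 40, however. Section 12.2 makes an explicit allowance for dropout and does not invoke the model to justify a smaller one, and the primary test is the group-by-time contrast at Visit 4, where early leavers supply the least information.

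**The power loss may look larger.** Exact calculations at 58% versus 25% fall from 57.1% to 52.5% (Pearson) and from 42.9% to 38.1% (Fisher) between 18 and 17 per arm, which suggests 4 to 5 points. Much of that is the discreteness of small 2×2 tables: exact Pearson power is 57.1% at 18 per arm but 56.3% at 20. The smooth calculations, at 2.4 to 2.6 points, describe the cost better.

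**Two participants in a pilot is trivial.** The trial is called a pilot, and the correction changes neither conduct nor analysis. That is a fair argument about severity. It does not make the sentence correct.

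**Perhaps 36 has another basis.** Read as a per-arm number, 36 would give 82.5% power for the responder rates, but the total would then be 72 before dropout and 72/0.85 = 84.7, so 85 (86 for equal arms) after it; the stated 20 per arm contradicts that reading. A gain from repeated measures could also bring 36 close: averaging three visits at an assumed within-patient correlation of 0.6 with d = 0.8 gives 36 in total. The plan states no correlation, and its primary test is the single Visit 4 contrast.

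**Conclusion.** Wrong as written; minor. The stated 36, 15% and 40 cannot all hold. Expected Visit 4 completers are 34, two short, and 40 corresponds to 10% dropout. On the plan's own effect assumptions the shortfall costs about 2 to 3 points of power. That treats each dropout as fully lost, so it is an upper figure for this analysis to the extent that the mixed model recovers information.

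A reader might infer that recruiting 43 or 44 would put the sample size right. It would settle the dropout arithmetic only. As a total, 36 gives about 52% power at 58% versus 25%, so the target itself does not carry the claimed power. That is the larger weakness in section 12.2, and it is separate: the dropout step would be wrong even if 36 were fully justified. The conclusion rests on reading 36 as a total, which the 20-per-arm figure implies but the text does not spell out.

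**What to change.** Keep N = 40 and replace the closing sentence of section 12.2 with wording such as:

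> *At 15% dropout, N=40 leaves 34 participants (17 per arm) completing Visit 4; 36 complete only if dropout is 10% or less.*

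Then state the power recomputed at 34 completers, naming the test and the assumptions: 49.7% for 58% versus 25% by the two-sided normal approximation, or 61.9% for d = 0.8 by t-test. If the sponsor wants credit for partial data in the mixed model, give the within-patient correlation and the calculation.

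In the same rewrite, correct the claim of more than 80% power at 36 and say whether 36 is a total or a per-arm number.

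The cost is a few sentences in one section. Enrolment, conduct and analysis do not change; the stated power becomes less favourable.

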12.3 Final Analysis

Descriptive statistics including measures of central tendency, dispersion and appropriate visualization approaches (e.g., box plots and spaghetti plots) will be performed on each outcome variable (pain scores, and outcomes in secondary and exploratory objectives) by time points and groups. This will be done to ascertain distributional characteristics and ensure that the assumptions (e.g., normality) associated with the planned statistical procedures are met. When necessary, transformations will be performed. All analyses will be done in SAS and will follow an intent-to-treat philosophy.

The main goal of the statistical analyses is to compare the changes in study primary and secondary endpoints between groups to evaluate efficacy of Erenumab. For the primary objective, the generalized Linear Mixed Models (GLMM) with binomial distribution will be used to assess the efficacy of Erenumab on the primary endpoint (i.e., at least 30% reduction in pain score; yes/no). The fixed effects included in the models will be treatment group (intervention versus placebo), time (dummy coded from baseline to visits 2-4), and the interaction terms of group by time. The random effects include the participants to account for correlations between repeated measures. The primary hypothesis will be tested by evaluating the interaction term of group and time from baseline to visit 4. In the meantime, the Erenumab efficacy from baseline to visits 2 and 3 will be evaluated through the interaction terms at the corresponding time points. The secondary objective of the difference in change (>30% reduction) from baseline to visit 5 will also be evaluated using the similar GLMM model with the corresponding time (baseline, V2-V5), group and interaction terms between time and group. The interaction of time (baseline to V5) and group will be evaluated to test the hypothesis. The difference from V4 to V5 will also be evaluated by contrast estimation from the model. We will use a significance level of twosided α < 0.05 as primary hypothesis test.

Separate linear mixed models will be applied to test other secondary objectives (e.g., monthly mean pain scores, measures of daily activities and functions, etc.) and exploratory objectives (e.g., QST measures) where the outcome variables are continuous. The model and testing will be the same as described in the above primary objective. The use of mixed models will provide flexibility with regard to assumptions related to the covariance structure of the residuals and the presence of missing data for the repeated measures.

Descriptive statistics for safety measures will also be calculated. We will collect the following data for descriptive purposes and, if necessary, to use as covariates: Demographic information (age and race/ethnicity), rescue medication history, psychological factors and perceived change in overall status (PGIC).

Missing Data

Participants may miss specific data points for a variety of reasons such as a missed visit, early withdrawal from the study, or inability to evaluate an endpoint at a time point. If participants miss entering data in the DSD, the missing data will be imputed by the mean of observed daily data if the missing days are less than 80% within a month. If the missing days are more than 80%, the monthly measurement from the previous month will be carried forward to replace the missing value for continuous endpoints.

If there is significant dropout, we will identify baseline characteristics that differ between those dropped out and retained. Maximum likelihood methods will be used for primary analyses, which address non-informative dropout [missing at random (MAR)]. If "informative" dropout is present, we will consider sensitivity analyses that add these relevant baseline covariates to make the MAR assumption more plausible [50]

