3 OBJECTIVES

3.1 Study Objectives

Primary Objective

To investigate the efficacy of Erenumab compared to placebo on the proportion of subjects who achieved at least 30% reduction in monthly average daily pain score from baseline to the end of treatment period.

Secondary Objectives

To investigate the efficacy of Erenumab compared to placebo on the reduction in monthly average daily pain score from baseline to the end of treatment period.

To investigate the efficacy of Erenumab compared to placebo on the proportion of subjects who achieved a least 30% reduction in the monthly average daily pain score from baseline to Visit 5 (follow-up/final visit).

To determine the efficacy of Erenumab using functional measures related to TNP impact in daily activities, disability and emotional functioning measured by questionnaires (GCPAs, HADS, PGIC and PENN Facial Pain Scale).

Exploratory Objectives

To explore changes in pro-inflammatory and anti-inflammatory cytokines from plasma/serum.

To determine the influence of Erenumab in nociceptive processing and sensitization using QST.

To determine the influence of Erenumab on PAF.

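### The primary question is about responder proportions, but section 12.3 tests a coefficient of a participant-random-effect GLMM and names no link, effect measure or conversion to proportions

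*Combined protocol and SAP*

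**What the plan says.** Section 3.1 sets the primary objective as efficacy "on the proportion of subjects who achieved at least 30% reduction in monthly average daily pain score from baseline to the end of treatment period". Section 12.1 states the hypothesis the same way: a higher proportion of responders on erenumab. Section 12.2 plans on a Cohen's d of 0.8 or an odds ratio of 4.2, and explains this as meaning that "about 58% of the participants in intervention group will reach at least 30% reduction in pain scores at the end of treatment", against 25% on placebo.

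For the analysis, section 12.3 says that "the generalized Linear Mixed Models (GLMM) with binomial distribution will be used to assess the efficacy of Erenumab on the primary endpoint". Fixed effects are group, time and their interaction, with baseline and Visits 2 to 4 as the levels of time. On correlation it says: "The random effects include the participants to account for correlations between repeated measures". The test is then fixed: "The primary hypothesis will be tested by evaluating the interaction term of group and time from baseline to visit 4". The Visit 5 responder objective uses a similar model with Visit 5 added. The missing-data text relies on maximum likelihood under missing at random.

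Section 12.3 also plans descriptive statistics for each outcome by time point and group. Nowhere does the document give the link function, the effect measure to be reported, the size of the random-effect variance, or a between-arm contrast of proportions with a confidence interval.

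**The concern.** A proportion of subjects is a population quantity, and so is the odds ratio formed from two such proportions. A logistic model with a participant random intercept conditions on the participant. Its group coefficient compares the odds of response on the two arms for people with the same value of the random intercept. The two odds ratios agree only when the random-intercept variance is zero or there is no effect. Otherwise the subject-specific one is further from 1, and the gap grows with the variance.

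Correlation is to be expected here, because every monthly yes/no outcome is measured against the same baseline mean, and the plan includes the random effect for that reason. Two things are at stake. The estimate that comes out of the primary model would not be the quantity in the objective. And anyone who set a fitted odds ratio beside the 4.2 in section 12.2 would be comparing two different scales. For a 40-person pilot meant to lay the ground for later work, the effect size carries as much weight as the p-value.

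**Working it through.** **Inputs from the documents.** Responder rates of 58% and 25%, odds ratio 4.2 and d = 0.8 (section 12.2); binomial mixed model with a participant random effect, baseline among the time levels, and the baseline-to-Visit-4 interaction as the tested term (section 12.3).

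**Assumptions.** Logit link; a normal random intercept with standard deviation s, the same in both arms. The latent intraclass correlation (ICC) is s²/(s² + π²/3). No value for it is in the documents, so a range is shown.

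**1. Reproduce the planned odds ratio.** From the proportions: (0.58 × 0.75)/(0.25 × 0.42) = 0.435/0.105 = 4.14. From d: exp(0.8 × π/√3) = 4.27. In reverse, odds of 4.2 × (0.25/0.75) = 1.4 give 1.4/2.4 = 58.3%. The planned 4.2 is therefore the marginal (population) odds ratio of 58% against 25%, a difference of 33 percentage points.

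**2. Check that the named coefficient can be estimated.** A reduction from baseline measured at baseline is zero, so every participant is a non-responder there. In one simulated data set with the baseline row included and the baseline log-odds set at −40, the log-likelihood was −68.833 for Visit 4 interaction values of −5, 0, 1.4, 3 and 6 alike. That equals the maximum from the post-baseline data alone. The interaction has no finite, identified estimate. The rest of the working therefore leaves baseline out and uses the group contrast at Visit 4.

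**3. Subject-specific odds ratio for the planned proportions.** For each ICC, s = √[ICC/(1 − ICC) × π²/3]. Solve for the log-odds b₁ and b₀ at which the logistic function of (b + s·z), averaged over a standard normal z, equals 0.58 and 0.25. The subject-specific odds ratio is exp(b₁ − b₀). At ICC 0.5, s = √3.290 = 1.814, b₁ = 0.503, b₀ = −1.686, and exp(2.189) = 8.9.

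**4. The reverse reading.** Hold placebo at 25% and take a subject-specific odds ratio of 4.2. The erenumab proportion is the average of the logistic function of (b₀ + ln 4.2 + s·z).

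| Assumed latent ICC | Subject-specific OR for 58% vs 25% | Erenumab responders implied by a subject-specific OR of 4.2 |
|---|---|---|
| 0 | 4.14 | 58% |
| 0.1 | 4.6 | 56% |
| 0.2 | 5.3 | 53% |
| 0.3 | 6.1 | 51% |
| 0.5 | 8.9 | 46% |
| 0.7 | 17.7 | 41% |
| 0.8 | 34.4 | 37% |

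For orientation, ICC 0.3 corresponds to a month-to-month correlation of the yes/no outcome of about 0.19 to 0.22, ICC 0.5 to about 0.33 to 0.36, and ICC 0.8 to about 0.6.

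**5. Behaviour at this sample size.** The model was fitted by maximum likelihood to 60 simulated trials per ICC, with 20 per arm and Visits 2 to 4 only. The Visit 2 and 3 rates were assumed: 45% and 52% on erenumab, 20% and 23% on placebo. The median fitted Visit 4 odds ratio was 6.6 (interquartile range 3.2 to 10.5) at ICC 0.3, 13.3 (6.5 to 28.6) at ICC 0.5 and 30.9 (7.7 to 106.4) at ICC 0.8. These figures depend on the assumed rates and on few runs. They show how unstable the odds ratio is, not what the trial will find.

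**The case against.** The strongest reply is that section 12.3 specifies a test, not a reported odds ratio. It names no link and nowhere proposes to set a fitted odds ratio beside 4.2. A reader might infer from the table that the trial would report an odds ratio of 9 to 34 where the data show 4. The documents do not support that. Those values need an ICC of 0.5 to 0.8, which is the upper part of an assumed range, and they arise only after baseline has been removed from the written model. At low correlation the gap is small. This part of the objection stands, and the figures are given as a range for that reason.

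A reader might also infer that the primary test is invalid. It is not invalid on this ground. If the random intercept has the same distribution in both arms, no subject-specific effect means no difference in proportions, and the direction of any effect agrees. The coefficient therefore still bears on the hypothesis of a higher proportion. This stands too.

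Finally, the planned descriptive statistics by time and group would probably show the responder proportion in each arm. That is true, but the plan attaches no between-arm contrast and no interval to them, and they lie outside the likelihood model that the plan relies on for missing data. The silence about link and effect measure is part of the gap and does not answer it.

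**Conclusion.** The mismatch is real, and it concerns the estimate and how it is read. The objective, hypothesis and sample size are in responder proportions, while the primary analysis rests on a subject-specific coefficient with no route back to proportions. Under a logit link with a normal random intercept common to both arms, a true 58% against 25% corresponds to a subject-specific odds ratio of about 4.6 at ICC 0.1, 6.1 at 0.3, 8.9 at 0.5 and 34 at 0.8, against a marginal 4.14. The direction holds for any positive variance; the size rests wholly on an ICC that the documents do not give. The problem with baseline in the yes/no model is a separate defect, and repairing it alone would still leave a subject-specific odds ratio. The plan should be changed on this point, but the point does not by itself undermine the test of no effect.

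**What to change.** In section 12.3:

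- State the link.
- Model only the post-baseline months, by maximum likelihood, so that the missing-at-random handling is kept.
- Define the primary estimate as the responder proportion per arm at Visit 4, averaged over the random intercept, with the between-arm difference and its 95% CI.
- Define the Visit 5 responder estimate in the same way.

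In section 12.2, label the odds ratio of 4.2 as marginal.

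If a marginal model fitted by GEE is preferred, use a small-sample correction and say that unweighted GEE needs stronger missing-data assumptions than the likelihood approach now in the plan.

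The cost is some wording and a few more lines of SAS, with no new data and no change in sample size. The effect measure will look less striking, and the change does not buy precision. With 20 per arm and complete data, the simple standard error of the difference is √(0.58 × 0.42/20 + 0.25 × 0.75/20) = 0.147, so the interval around 33 points would be about ±29 points (1.96 × 14.7).

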3.2 Study Outcome Measures

3.2.1 Primary

The primary end point will be to achieve >=30% reduction (Yes/no) in monthly (28 days) average pain score from baseline to Visit 4 (the last monthly treatment cycle), compared to placebo. The daily pain intensity score will be measured on a 11-point (0-10) numeric rating scale (NPRS) and reported in the Daily Symptom Diary (DSD). The monthly mean pain intensity score will be determined from baseline (4 weeks/28 days), for each month during the 12 weeks of treatment.

The monthly mean pain intensity score will be calculated if a participant has at least 80% compliance with the DSD.

A relevant decrease in chronic pain showing a beneficial effect will be a reduction of >=30% from baseline in the average pain intensity score [29, 30].

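### The primary test is a baseline-to-Visit-4 interaction on a responder outcome nobody can meet at baseline, so as written it cannot detect a treatment effect

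*Combined protocol and SAP*

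**What the plan says.** Section 3.2.1 defines the outcome: "The primary end point will be to achieve >=30% reduction (Yes/no) in monthly (28 days) average pain score from baseline to Visit 4". Section 12.1 states the hypothesis as a higher responder proportion on erenumab than on placebo at the end of treatment.

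Section 12.3 gives the model: "the generalized Linear Mixed Models (GLMM) with binomial distribution will be used to assess the efficacy of Erenumab on the primary endpoint". The fixed effects are group, "time (dummy coded from baseline to visits 2-4), and the interaction terms of group by time". On correlation it says: "The random effects include the participants to account for correlations between repeated measures". The primary test is then named: "The primary hypothesis will be tested by evaluating the interaction term of group and time from baseline to visit 4". The interactions at Visits 2 and 3 are to be read in the same way.

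The Visit 5 responder analysis is set up "using the similar GLMM model with the corresponding time (baseline, V2-V5), group and interaction terms between time and group". That list shows that baseline is a modelled response level, and not only the comparator inside the endpoint definition. The only contrast the section names is Visit 4 to Visit 5. It names no between-group contrast at Visit 4.

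**The concern.** Responder status measures change from baseline, so at baseline it is either No for every participant or undefined. A group-by-time interaction referenced to baseline asks whether the between-group log odds ratio at Visit 4 differs from the one at baseline. With no responders in either arm at baseline, that second quantity does not exist.

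The section 12.1 hypothesis is a between-group difference at Visit 4, which is a different parameter. If the named test is run, the software will fail to converge or return a p-value near 1, even if erenumab works well. The analyst would then have to choose a replacement test after seeing the failure.

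**Working it through.** **Inputs.** Section 12.2: 58% versus 25% responders, d = 0.8 or OR = 4.2, two-sided alpha 0.05, 36 evaluable (18 per arm), 40 recruited (20 per arm). Section 12.3: the model above. The baseline counts of 0/n in each arm follow from the endpoint definition.

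**The plan's own figure.** The plan gives power above 80% at n = 36 and does not tie it to the interaction test. The effect sizes agree with each other: (0.58/0.42)/(0.25/0.75) = 4.14, and exp(0.8π/√3) = 4.27. The power is not reproduced by a two-group comparison. For two proportions with 18 per arm:

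- Null SE = √(2 × 0.415 × 0.585/18) = 0.164.
- Alternative SE = √(0.58 × 0.42/18 + 0.25 × 0.75/18) = 0.155.
- Power = Φ((0.33 − 1.96 × 0.164)/0.155) = 52%. With 20 per arm it is 57%.

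That is a separate matter. Here it only sets the benchmark for a test that uses the Visit 4 data properly.

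**Algebra.** Write logit P = α + γG + τₜ + δₜG + participant effect, with baseline as reference.

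- Baseline cells: α on placebo and α + γ on erenumab.
- Visit 4 log odds ratio: γ + δ₄.
- With 0/n in both baseline cells, the likelihood pushes α to minus infinity. Any finite γ then fits baseline perfectly, for every value of the participant effect.
- Now set δ₄ = 0. Take γ equal to the Visit 4 log odds ratio, and let δ₂, δ₃ and the τₜ adjust. Every post-baseline cell is fitted exactly as before, and the baseline contribution still tends to 1.
- The two maximised likelihoods are equal, so the 1-df likelihood-ratio (LR) statistic is 0 for any Visit 4 data.

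**Worked example.** Take 20 per arm, with Visit 4 responders 12/20 versus 5/20 (illustrative, close to 58% versus 25%) and no participant effect, to keep the arithmetic visible. The log OR is ln[(12/8)/(5/15)] = ln 4.5 = 1.50.

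| Quantity | Baseline logit −10 | Baseline logit −20 |
|---|---|---|
| LR ≈ 2 × 20 × (e^(logit + 1.5) − e^logit) | 0.006 | 3 × 10⁻⁷ |
| Interaction SE ≈ √(2/(20 e^logit) + 0.475) | 47 | about 7,000 |
| Wald z = 1.50/SE | 0.03 | 0.0002 |

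The 0.475 is the Visit 4 part, 1/12 + 1/8 + 1/5 + 1/15. Used alone it gives SE = √0.475 = 0.69 and z = 1.50/0.69 = 2.18. The interaction SE has no finite limit; its printed value depends only on where the optimiser stops.

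**Simulation.** The full random-intercept logistic model was fitted by maximum likelihood to 150 simulated trials per scenario. Assumptions that are not in the plan: random-intercept SD 1.5, and equal responder rates at Visits 2 to 4 within an arm.

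| True rates | n per arm | Interaction, Wald rejections | Visit 4 contrast, same fit |
|---|---|---|---|
| 58% vs 25% | 18 | 0/150 | 43% |
| 58% vs 25% | 20 | 0/150 | 53% |
| 90% vs 25% | 18 | 0/150 | 86% |
| 90% vs 25% | 20 | 0/150 | 85% |
| 25% vs 25% | 18 | 0/150 | 3% |
| 25% vs 25% | 20 | 0/150 | 6% |

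The likelihood-ratio test never rejected either. Its statistic was 0 apart from optimiser error (at most 0.2, with one fit non-numeric).

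**Sensitivity.** Adding 0.5 to each cell makes the interaction finite, but the two baseline cells dominate its variance. With 18 per arm, SE = √(4.108 + 0.216 + 0.271) = 2.14. The log OR is ln 4.14 = 1.42, and power is about 10%. On an identity link the interaction equals the Visit 4 risk difference, with power of 57% (18 per arm) to 61% (20 per arm).

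**The case against.** The strongest reply is that the result is conditional. Section 12.3 states no link, and on an identity link the interaction is informative. It does not say how baseline is coded; if baseline is missing, those rows drop out and the fit uses post-baseline visits only. The endpoint, time point, comparison and direction are fixed in sections 3 and 12.1, and the Visit 4 contrast can be estimated from the same model. On this view the plan names the wrong coefficient but keeps its estimand.

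Part of this stands. The endpoint and time point are not lost, so the damage to pre-specification is partial. The fault lies in the named test and not in the data.

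The rest does not rescue the test:

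- **Link and estimation.** The odds ratio in section 12.2 and the choice of maximum likelihood under Missing Data in section 12.3 point to an ordinary logit fit. No identity link appears anywhere, and it sits badly with a participant random intercept when the baseline probability is 0.
- **Baseline as missing.** This contradicts the listed levels "with the corresponding time (baseline, V2-V5), group and interaction terms between time and group". It also makes the named interaction non-estimable, or turns it into a change from Visit 2 to Visit 4. That change is zero for an effect constant from Visit 2 onwards, so it does not test the section 12.1 hypothesis.
- **Correction of empty cells.** The plan mentions none, and the one tried leaves about 10% power.

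**Conclusion.** The concern holds. With a logit link, maximum likelihood and baseline responder status coded No, the named primary test has a likelihood-ratio statistic of 0 and no power, even at 90% versus 25% responders. The algebra carries this conclusion. The simulation confirms it under an assumed random-intercept SD and assumed visit pattern.

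The baseline-referenced responder interactions at Visits 2, 3 and 5 share the fault. The linear mixed models for continuous outcomes do not, because their baseline values vary. The Visit 4 to Visit 5 contrast compares post-baseline cells only and is also unaffected.

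This must be fixed before unblinding, because it concerns the one test on which the primary conclusion rests.

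**What to change.** In section 12.3:

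1. Fit the responder model to post-baseline visits only: Visits 2 to 4 for the primary analysis and Visits 2 to 5 for the follow-up secondary. Remove baseline as a level of time.
2. State the link (logit) and the estimation method.
3. Name the erenumab-versus-placebo contrast at Visit 4 as the primary test, two-sided at 0.05, reported as an odds ratio with 95% CI. Define the Visit 2, 3 and 5 comparisons in the same way.
4. Enter the 28-day baseline mean pain score as a continuous covariate.
5. Give the continuous outcomes their own model statement. They now borrow the primary model by cross-reference, and should not lose baseline as a time level by accident.

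Items 1 to 3 cure the defect. Item 4 keeps the baseline information in the model in a usable form. A risk difference with 95% CI would also help readers; from a logit mixed model it needs a stated averaging step over participants and covariates.

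The cost is SAP wording, with no new data and no extra participants. The corrected test would still have only about 52% to 57% power for 58% versus 25% by the two-proportion calculation, so the sample-size statement needs its own review.
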